### 3.3 General Considerations

Data for Substudy 1 is presented separately for part A, B and C. For part A data is presented by dose level and overall. For part B, data is presented in separate tables for tumour type, and by dose level and overall (in each column of the tables). For part C, data is presented in separate tables for indication or by dose level (as applicable at the time).

#### 3.3.1 General Study Level Definitions

The general principles described below are followed throughout the study:

- Continuous endpoints are summarised by the number of observations, mean, standard deviation (Std Dev), median, upper, and lower quartiles (as applicable), minimum, and maximum. For data that requires log-transformation, it is more appropriate to present geometric mean, Coefficient of Variation (CV), median, minimum, and maximum. Categorical endpoints are summarised by frequency counts and percentages for each category.
- If data are available for less than three participants, no summary statistics other than minimum, maximum, and number of observations are presented.
- Unless otherwise stated, percentages are calculated out of the analysis set total (excluding efficacy and exposure) and for dose cohort by time point and tumour type as appropriate.
- For continuous data, descriptive summary statistics (mean, median, Std Dev, standard error, Confidence Intervals [CIs]) are rounded to one additional decimal place compared to the original data. Minimum and maximum are displayed with the same accuracy as the original data.
- For categorical data, percentages are rounded to 1 decimal place.
- SAS® version 9.4 (as a minimum) is used for all analyses.

- Baseline is the last non-missing value obtained prior to the first dose/administration of any IP and any information taken after first dose/administration of IP is regarded as post-baseline information. If two visits are equally eligible to assess participant status at baseline (e.g., screening and baseline assessments both on the same date prior to first dose/administration with no washout or other intervention in the screening period), the average is taken as the baseline value. For non-numeric laboratory tests (i.e., some of the urinalysis parameters) where taking an average is not possible then the best value is taken as baseline as this is the most conservative. In the scenario where there are two assessments on Day 1 prior to first dose, one with time recorded and the other without time recorded, the one with time recorded is selected as baseline. Where safety data are summarised over time, study day is calculated in relation to date of first treatment. For assessments on the day of first dose where time is not captured, a nominal pre-dose indicator, if available, serves as sufficient evidence that the assessment occurred prior to first dose. Assessments on the day of the first dose where neither time nor a nominal pre-dose indicator are captured is considered prior to the first dose if such procedures are required by the protocol to be conducted before the first dose. If no value exists before the first dose/administration, then the baseline value is treated as missing.
- In all summaries, change from baseline endpoints are calculated as the post treatment value minus the value at baseline. The percentage change from baseline is calculated as  $(\text{post-baseline value} - \text{baseline value}) / \text{baseline value} \times 100$ . For any endpoint subjected to log transformation, the change from baseline calculated and summarised on the log scale are back-transformed and presented as a ‘baseline scaled ratio’ (BSR). Percentage change is then calculated as  $(\text{BSR} - 1) \times 100$ .
- Unless stated otherwise, two-sided CIs are produced at 90%.
- For the purposes of summarizing safety data assessed at visits, in addition to baseline data, only on treatment data is included in the summary tables. On treatment data is defined as data after the first dose of investigational product (IP) and with assessment date up to and including the date of last IP + 97 days (to consider the  $\pm 7$  days visit window for the post-treatment follow-up visit planned 90 days after the last dose), and prior to the start of any subsequent cancer therapy.

### 3.3.2 Visit Window

For safety, time windows are defined for any presentations that summarize values by visit. The following conventions apply:

- The time windows are exhaustive so that data recorded at any timepoint has the potential to be summarised. Inclusion within the time window is based on the actual date and not the intended date of the visit.
- All unscheduled visit data have the potential to be included in the summaries.

- The window for the visits' following baseline is constructed in such a way that the upper limit of the interval falls halfway between the two visits (the lower limit of the first post-baseline visit is Day 2). If an even number of days exists between two consecutive visits, then the upper limit is taken as the midpoint value minus 1 day.

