### **Substudy 1:**

The first 11 visit windows for data between scheduled assessments in this study are:

- Day 2, visit window 2-4
  - Day 8, visit window 5-11
  - Day 15, visit window 12-18
  - Day 22, visit window 19-25
  - Day 29, visit window 26-32
  - Day 36, visit window 33-39
  - Day 43, visit window 40-52
  - Day 64, visit window 53-73
  - Day 85, visit window 74-94
  - Day 106, visit window 95-115
  - Day 127, visit window 115-136
- Visit windowing are done separately for each assessment based on the schedule of events specific to that assessment
  - Should visit date be missing (due to partial or missing dates), then visits are assigned to the nominal visit at which that assessment was recorded, and no windowing is performed.
  - For visit-based summaries, if there is more than one value per participant within a time window then the closest value to the scheduled visit date is summarised, or the earlier, in the event the values are equidistant from the nominal visit date. In the scenario that a complete visit date falls into the same visit as one that has been assigned due to missing data, the visit with the complete date is summarised. The listings highlight the value for the participant that contributed to the summary table, wherever feasible. Note: in summaries of extreme values, all post baseline values collected are used including those collected at unscheduled visits regardless of whether the value is closest to the scheduled visit date.
  - For summaries at a participant level, all values are included, regardless of whether they appear in a corresponding visit-based summary, when deriving a participant level statistic such as a maximum.

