##### ECOGs

The number and percentage of each participant in each ECOG category will be displayed by each timepoint.

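### As written, the SAP's safety visit windows place end-of-treatment and follow-up values of participants who have stopped AZD8853 in rows labelled as on-study dosing visits

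*SAP*

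**What the plan says.** Four rules act together.

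- **What is kept.** SAP 3.3.1 limits by-visit safety summaries to baseline and on-treatment data. It defines the latter as data after first dose, "with assessment date up to and including the date of last IP + 97 days" and "prior to the start of any subsequent cancer therapy". The stated purpose of the 97 days is to accommodate the 90-day visit with its 7-day window.
- **Time origin.** SAP 3.3.1: "study day is calculated in relation to date of first treatment".
- **Where values go.** SAP 3.3.2: "The time windows are exhaustive so that data recorded at any timepoint has the potential to be summarised", and "Inclusion within the time window is based on the actual date and not the intended date of the visit". The nominal visit is used only if the visit date is missing. If several values fall in one window, the one nearest the scheduled day is summarised.
- **Which rows exist.** The Substudy 1 list opens "The first 11 visit windows for data between scheduled assessments in this study are" and runs from Day 2 to Day 127, for example "Day 106, visit window 95-115". Every entry is a visit in protocol Table 13. From Day 43 on, each is a dosing day.

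Protocol Table 14 adds three visits counted from other anchors: EOT, 30 (±7) days after EOT, and 90 (±7) days after last dose. Vital signs with weight and ECOG are collected at all three. Chemistry, haematology, coagulation and urinalysis are collected at EOT and 30 days, and ECG at EOT only.

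**The concern.** A visit counted from EOT or last dose has no fixed study day, so fixed study-day windows cannot represent it. The SAP nevertheless admits these values and gives them no row of their own. With a known date, they fall into whichever on-study window covers that day.

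A row read as the state of participants at Cycle 5 or 6 would then mix those still being dosed with those who stopped weeks earlier, many of them after progression. A fall in weight or a worse ECOG grade after stopping would look like a change under continued dosing. The ECOG output has this exposure directly: "The number and percentage of each participant in each ECOG category will be displayed by each timepoint". Vital signs are also summarised and box-plotted by visit (SAP 4.2.1.6.2), and laboratory changes are graphed by visit (SAP 4.2.1.3.2). Conversely, an EOT value that shares a window with a value nearer the scheduled day disappears from the by-visit table.

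**Working it through.** **1. The plan's own windows.** SAP 3.3.2 ends each window halfway to the next visit, less one day if an even number of days lies between the two visits.

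- Reading *even* as the visit-to-visit gap: Day 2 to 8 has gap 6 and midpoint 5, so the upper limit is 4. Day 8 to 15 has midpoint 11.5, so 11. This reproduces 6 of the 11 windows (Days 2 to 36). From Day 43 the rule gives upper limits 53, 74, 95, 116 and 137; the SAP lists 52, 73, 94, 115 and 136.
- Reading it as days strictly between visits reproduces only the Day 64, 85 and 106 windows in full.
- Day 115 is in two listed windows: 95-115 (Day 106) and 115-136 (Day 127).

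The example below gives the same rows under either reading.

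**2. One participant, two doses (Days 1 and 22), EOT on Day 49.**

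- EOT: Day 49, in 40-52, tabulated as Day 43 (Cycle 3 Day 1, a dose not given).
- 30-day visit: 49 + 30 = Day 79, in 74-94, tabulated as Day 85.
- 90-day visit: 22 + 90 = Day 112, in 95-115, tabulated as Day 106. The cut is 22 + 97 = Day 119, so the value is kept.

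**3. Other stopping times.** The interval from last dose to EOT is not documented; 7 to 28 days is assumed. The 30-day visit is EOT + 23 to 37 days, and the 90-day visit is last dose + 83 to 97 days.

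| Last dose | EOT: days (rows) | 30-day: days (rows) | 90-day: days (rows) |
|---|---|---|---|
| Day 1 | 8-29 (8 to 29) | 31-66 (29 to 64) | 84-98 (85, 106) |
| Day 22 | 29-50 (29 to 43) | 52-87 (43 to 85) | 105-119 (106, 127) |
| Day 43 | 50-71 (43, 64) | 73-108 (64 to 106) | 126-140 (127 or later) |
| Day 64 | 71-92 (64, 85) | 94-129 (85 to 127) | 147-161 (past Day 136) |
| Day 85 | 92-113 (85, 106) | 115-150 (106 or later) | 168-182 (past Day 136) |
| Day 106 | 113-134 (106, 127) | 136-171 (127 or later) | 189-203 (past Day 136) |

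The rows affected therefore depend on when the participant stopped.

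**4. Size, by hand, for the Day 106 vital-sign and ECOG row.** All rates here are assumptions. Of 100 participants, 50 stop after two doses, 25 stop after five doses (last dose Day 85) and 25 continue. Of those who stop, 40% start new therapy 7 to 59 days after EOT. Off-drug means more than 21 days after last dose. Visit dates are uniform over ±7 days, and Day 115 is counted in the Day 106 row.

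- Early stoppers: the 90-day visit falls on Days 105-119, and 11 of those 15 days are at or before Day 115. With EOT at Day 43 or 44, new therapy starts by Day 103 and removes all of the 40%. Contribution: 50 × 0.6 × 11/15 = 22.
- Later stoppers contribute 25 EOT values, and continuing participants 25.
- EOT 21 days after last dose: the later stoppers' EOT falls on Day 106 and is not counted as off-drug. Share = 22/72 = 31%.
- EOT 22 days after last dose: those 25 count. Share = 47/72 = 65%.

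One day in an undocumented interval doubles the figure. Simulations that spread EOT over 7 to 28, 14 to 27 or 21 to 34 days after last dose, with early stopping at 30% to 60% and new therapy at 0% to 70%, gave about 25% to 66%. This is not a bound. With EOT fixed at 21 days, 30% early stopping and 70% new therapy, the share is 6.6/(6.6 + 35 + 35) = 9%, where 6.6 = 30 × 0.3 × 11/15. With EOT at 22 days, 60% and 0%, it is (44 + 20)/(44 + 20 + 20) = 76%, where 44 = 60 × 11/15.

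**The case against.** The best defence is that the SAP is incomplete here rather than wrong. The list is only of the first 11 windows, and SAP 3.3.2 says windowing follows each assessment's own schedule, which could include the Table 14 columns. The table shells are not in the documents and may carry EOT and follow-up rows. This softens the point but does not remove it. Neither sentence gives a rule for these visits, and the rules that are stated send a dated value to a study-day window.

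Other parts of the defence stand.

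- The primary safety endpoints are incidences. Extreme-value and participant-level summaries use all values regardless of window, and no cohorts are compared.
- Calling data to last dose + 97 days on-treatment is a deliberate definition that matches the adverse event period in SAP 4.2.1.2.
- Missing dates are handled by nominal visit, and the new-therapy cut removes some off-drug values.
- The documents do not show that drug effect has ended 21 days after a dose; PK is still sampled at 90 days. The 21-day threshold above is a device for counting only.

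A reader might infer that every by-visit safety summary is distorted, or that only Cycles 4 to 7 are affected. Table 14 rules out the first, since there is no 90-day laboratory panel other than a pregnancy test and no ECG after EOT. The table of stopping times rules out the second.

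**Conclusion.** The point holds as a labelling fault in by-visit safety tables. Under SAP 3.3.1 and 3.3.2 as written, dated EOT and follow-up values of participants who have stopped AZD8853 and not started new cancer therapy enter on-study visit rows. Where no value nearer the scheduled day competes, they are the values summarised.

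That placement follows from the SAP text and needs no assumption beyond the dates. The share of affected values does not: stopping times, EOT timing and new-therapy rates are all undocumented, so 25% to 66% for the Day 106 row is an illustration and should not be quoted as an estimate. A reader might also infer that the primary safety conclusions are compromised. The documents do not support that, because incidence, worst-value and adverse event outputs do not pass through these windows. The overlap at Day 115 is a separate, certain error in the same list.

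**What to change.** In SAP 3.3.2:

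1. Apply the study-day windows only to assessments before the EOT visit.
2. Summarise EOT, 30-day and 90-day follow-up as separate analysis visits, anchored to EOT or last dose, for each assessment that Table 14 schedules at that visit.
3. Assign unscheduled values after EOT to the nearest of these visits, so that the windows remain exhaustive.
4. Keep all values in the extreme-value and participant-level summaries, as now.
5. Remove Day 115 from one of its two windows, and state the midpoint rule so that it reproduces the list.

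The cost is a few SAP sentences, minor programming and up to three extra rows per table: three for vital signs and ECOG, two for most laboratory tables and one for ECG. No new data are needed.

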Week	1	1	1	2	3	4	5	6	7	10	13	16	19+	
Cycle Number and Cycle Day ^a	C1D1	C1D1	C1D2	C1D8 (±1D)	C1D15 (±1D)	C2D1 (±1D)	C2D8 (±1D)	C2 D15 (±1D)	C3D1 (±3D)	C4D1 (±3D)	C5D1 (±3D)	C6D1 (±3D)	C7D1-CnD1 (±3D)	
Part C: AZD8853 PK	X	X				X			X	X	X	X		10.8.5.1; Table 18
Study Treatment A	dministr	ation												
AZD8853 administration (Q3W)	X					X			X	X	X	X	Q3W	6.1
Part B only: CD8+	PET (sel	ect and v	alidated s	ites only)										
CD8+ PET Tracer Administration							X °							Appendix I
Whole body PET scan							X °							Appendix I

Any timing of safety assessment visit is relative to the day of most recent dosing (Day 1 of the latest cycle).

- c For Part A only.
- d Weight on Day 1 post-dose is not needed.
- To include CT or MRI slices through T12 and L3. Any timing of tumour assessment visit is relative to Cycle 1 Day 1.
- f Disease assessment should be performed on the week prior to next assessment cycle, always prior to dosing.
- g All collections must be pre-dose unless specified otherwise.
- h Sample can be taken at any point during study.
- Free T4 and T3 measured if TSH is abnormal or if clinical suspicion of an AE related to the endocrine system.
- A urine or serum pregnancy test is acceptable; if urine test is equivocal or positive then serum β-hCG testing should be performed for confirmation.
- Required for participants with a history of hepatitis B or hepatitis C.

If screening assessments have been performed within the 72 hours prior to Day 1, then the assessment does not need to be performed pre-dose on Day 1. All safety laboratory results must be reviewed by the Investigator or physician designee prior to administration of the scheduled dose of study intervention. Pregnancy testing for WOCBP is required on all days of dosing.

- Fresh paired biopsy samples will be taken as specified in all mandatory paired biopsy cohorts in Parts B but are optional for all other participants. If they are taken during screening they will not need to be taken for Cycle 1 Day 1 pre-dose.
- The second paired biopsy sample should be collected on Cycle 2 Day 8 (# days relative to Cycle 2 Day 8). For participants who are in the CD8+ PET cohort, the first and second biopsy should be taken within hours after the first and second CD8+ PET scan, respectively. This second biopsy must still be collected if not done within the time windows described.
- To be taken at time of second paired biopsy.

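### The SAP's date-based visit windows start at Day 2, so the Cycle 1 Day 1 post-infusion ECG and post-dose vital signs have no row in the by-visit safety summaries

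*SAP*

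**What the plan says.** SAP 3.3.2 sets the scope: "For safety, time windows are defined for any presentations that summarize values by visit". It assigns values by calendar date: "Inclusion within the time window is based on the actual date and not the intended date of the visit". It fixes the start of post-baseline windowing: "the lower limit of the first post-baseline visit is Day 2". The Substudy 1 list opens with "Day 2, visit window 2-4" and ends with the Day 127 window. The same section also claims full coverage: "The time windows are exhaustive so that data recorded at any timepoint has the potential to be summarised".

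SAP 3.3.1 settles the status of a reading taken after the infusion: "any information taken after first dose/administration of IP is regarded as post-baseline information".

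The protocol schedules such readings. Table 17 (10.8.2.1, Parts A, B and C) asks for an ECG at 0 hours after the end of infusion on Cycle 1 Day 1. Table 13 (10.1.2) has a Day 1 post-dose column with both ECG and vital signs marked. Its footnote waives only one item: "Weight on Day 1 post-dose is not needed".

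**The concern.** The statement that the windows are exhaustive and the Day 2 start cannot both hold once a post-baseline value is scheduled on Day 1. A programmer who follows the rule as written has nowhere to put the value. It cannot be baseline, because it follows the first dose, and no post-baseline window reaches back to Day 1.

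This is a first-in-human intravenous antibody, and changes in ECG and vital signs belong to the primary safety endpoints. The reading after the first infusion is the natural place to look for an acute shift in QTcF, blood pressure or pulse. If it has no row, the by-visit ECG means and changes from baseline contain no post-infusion value at all. A mean shift immediately after infusion would then not be visible in the tables designed to show mean shifts.

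**Working it through.** **Reproducing the SAP's windows.** The rule sets the lower limit of the first window at Day 2. Each upper limit is the midpoint between consecutive visits, less 1 day when the gap is even.
- Day 2 to Day 8: gap 6 (even), midpoint 5, minus 1 = 4. Window 2–4, as listed.
- Day 8 to Day 15: gap 7, midpoint 11.5, rounded down to 11. Window 5–11, as listed.
- The first six windows (Days 2 to 36) reproduce exactly. From Day 43 on, the listed upper limits (52, 73, 94, 115, 136) are each one day below what the rule gives (53, 74, 95, 116, 137). Day 115 lies in two windows (95–115 and 115–136). Neither slip affects Day 1.

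**Coverage.** Counting the listed windows that contain each study day from 1 to 136: Day 1 is in 0 of 11, and every day from 2 to 136 is in at least one. Day 1 is the only uncovered day.

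**Are the readings on Day 1?** Protocol 6.2.2 gives a standard infusion time of 1 hour and a ceiling of 4 hours, so an end-of-infusion ECG falls on Day 1 in ordinary clinic practice.

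**Does assessment-specific windowing help?** The SAP says "Visit windowing are done separately for each assessment based on the schedule of events specific to that assessment". Applying the rule to each schedule, with the Day 2 lower limit retained:
- ECG visits at Days 22, 43 and 127, with the next 12-weekly ECG at 127 + 84 = Day 211:
  - Day 22: (22 + 43)/2 = 32.5, giving 2–32.
  - Day 43: (43 + 127)/2 = 85, gap 84 (even), giving 33–84.
  - Day 127: (127 + 211)/2 = 169, gap 84 (even), giving 85–168.
- Vital signs, first post-baseline visit Day 8: (8 + 15)/2 = 11.5, giving 2–11.

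Both sets still start at Day 2.

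**Does nominal-visit assignment help?** SAP 3.3.2 uses the nominal visit only when the visit date is missing. A dated Day 1 value does not qualify.

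**What is left out.** After first dosing and up to Cycle 7 Day 1, Table 17 times four ECGs: Cycle 1 Day 1 at end of infusion, then Cycle 2, Cycle 3 and Cycle 7 Day 1, all three pre-dose. The omitted reading is 1 of 4, and it is the only one that follows an infusion. For vital signs, the Day 1 reading is the only one labelled post-dose in Table 13.

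**The case against.** The strongest reply is that a post-dose row is already implied. Table 13 puts the Day 1 pre-dose and post-dose columns under the same visit (V2), so the post-dose reading could be a timepoint within that visit, not a later visit that needs a window. SAP 4.2.1.7.1 speaks of ECGs scheduled both before and after dosing and of values assigned to the matching timepoint, and Cycle 1 Day 1 is the only scheduled post-dose ECG. The box plots in 4.2.1.6.2 and 4.2.1.7.2 are by timepoint. This shows that a post-dose row may well be intended, and it leaves open whether the box plots include the value. It does not override the stated Day 2 limit, and no sentence assigns a dated Day 1 post-dose value to a by-visit row.

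The reply is right about the limits of the damage. A reader might infer any of the following, and the documents support none of them:
- *A QTcF signal after infusion would be lost.* SAP 3.3.2 keeps all values in participant-level and extreme-value summaries. Maximum QTcF, maximum QTcF change and the listings therefore retain the reading, and clinically relevant ECG findings are also recorded as adverse events (Protocol 8.2.4).
- *The primary safety analysis fails.* Its measure in SAP Table 3 is the percentage of participants with clinically significant changes, which is a participant-level summary.
- *The remaining vital-sign data are all trough readings.* Days 8 and 15 are mid-cycle, and on later dosing days blood pressure and pulse have no stated time relative to the infusion.
- *Every other ECG is a pre-dose trough.* The end-of-treatment ECG is not tied to a dose.

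It is also no fault in itself that an extreme-value table can contain a value missing from a by-visit table; SAP 3.3.2 expressly allows it.

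**Conclusion.** The gap is real and contained. As written, the Day 1 post-infusion ECG and post-dose vital signs fall in 0 of 11 windows, so by-visit summaries and changes from baseline omit them for every participant in all three parts. For ECG, this removes the only reading timed after an infusion. For vital signs, it removes the only one labelled post-dose. Box plots are ambiguous. Listings, participant-level maxima and the QTcF categories are unaffected.

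The conclusion rests on a literal reading of the Day 2 limit and on the infusion ending on Day 1. That the end-of-infusion reading lies near peak concentration is an inference from the intravenous route, and the finding does not depend on it. The point merits correction because the tables affected are the ones that would show an average shift after the first infusion and the remedy is trivial.

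**What to change.** In SAP 3.3.2, add a Day 1 post-dose timepoint for ECG and vital signs, covering Day 1 after the start of the first infusion. Assign it by recorded time or by a nominal post-dose indicator, since date alone cannot separate it from the pre-dose value; SAP 3.3.1 already uses time and a nominal pre-dose indicator to identify baseline. Tabulate it and plot it as its own row, with change from baseline, and state that the box plots include it. Keep Day 2 as the lower limit of the next window.

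The cost is one line in the SAP and one extra row per table. No new data are needed, and no endpoint or analysis population changes. The same edit can remove the Day 115 overlap and align the limits from Day 43 onward with the stated rule.
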